4.11.2. CGM Variable and Analysis

The following variables derived from CGM will be summarized and compared between treatment groups by visit using MMRM model. The model will include the treatment, HbA1c stratum (<8.5% or ≥8.5%), baseline FBG, visit, and treatment by visit interaction. The LS

mean difference between treatment groups will be summarized. We are missing CGM documentation if visit intervals are longer than 4 weeks due to storage limitation in the receiver.

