## 7.2. Method of Treatment Assignment

Study participants who meet all criteria for enrollment will be randomized to open-label treatment at Visit 3. Assignment to treatment groups will be determined by a computer-generated random sequence using an interactive web-response system (IWRS). The IWRS will be used to assign open-label IP to each study participant. Site personnel will confirm that they have located the correct IP by entering a confirmation number found on the IP label into the IWRS.

To achieve between-group comparability for site factor, the randomization will be stratified by country, baseline HbA1c (<8.5%, ≥8.5%), country, SU (yes/no), and baseline BMI (<30, ≥30). The randomization scheme will be performed using IWRS, which will ensure balance between treatment arms.

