4.10.3.2. Hypoglycemia Events

Both the rate per 1 patient year and incidence of the following type of hypoglycemia events will be derived and analyzed: documented hypoglycemia, documented nocturnal hypoglycemia (occurs between bedtime and waking), and documented non-nocturnal hypoglycemia (occurs between waking and bedtime).

[Table BDCM.1](#) provides the summary of statistical method for hypoglycemia event related analysis. Additionally, severe hypoglycemia events will be listed, and incidence of severe hypoglycemia will be compared between treatments using Fishers' exact test.

Table BDCM.1. Hypoglycemia Event Related Analyses

Endpoint	Time Point*	Statistical Method
Rate of hypoglycemia events defined by glucose <54 mg/dL (3.0 mmol/L) and ≤ 70 mg/dL (3.9 mmol/L) 
 • Documented • Nocturnal • Non-Nocturnal 	0-12, 0-32, 12-32 weeks, post-treatment period (up to Visit 801)*	Negative binomial regression with treatment, baseline SU use (yes/no), baseline HbA1c, baseline hypoglycemia event rate with the same category of the dependent variable, log (exposure in year) as the offset in the model.
Incidence of hypoglycemia events defined by glucose <54 mg/dL (3.0 mmol/L) and ≤ 70 mg/dL (3.9 mmol/L) 
 • Documented • Nocturnal • Non-Nocturnal 	0-12, 0-32, 12-32 weeks, post-treatment period (up to Visit 801)*	Logistic regression with treatment, baseline SU use (yes/no), baseline HbA1c, baseline hypoglycemia event rate with the same category of the dependent variable in the model. Note that the logistic regression will be conducted when ≥10 patients with this event.

 • Proportion of patients with HbA1c <7% without nocturnal hypoglycemia event • Proportion of patients with HbA1c ≤6.5% without nocturnal hypoglycemia event 	0-32 weeks	Logistic regression with treatment, baseline SU/meglitinide use (yes/no), baseline HbA1c, and baseline nocturnal hypoglycemia event rate in the model.

Abbreviations: HbA1c = hemoglobin A1c.

Note: The hypoglycemia rate per year during defined period is calculated by the number of hypoglycemia within the period/number of days patient at risk within the period*365.25 days. The hypoglycemia incidence during defined period indicates if the patient has at least 1 hypoglycemia events within the period (Yes/No). The baseline hypoglycemia rate is the rate calculated between Visit 1 and Visit 3.

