4.11.2.1. Hypoglycemia

- Percentage and Duration (in minutes) of time per day where glucose values are within a hypoglycemic range (defined as ≤ 70 mg/dL [3.9 mmol/L]) during the nighttime period (defined as midnight to 0600 hours).
- Percentage and Duration (in minutes) of time per day glucose values are within a hypoglycemic range (defined as ≤ 70 mg/dL [3.9 mmol/L]) during a 24-hour period.
- Percentage and Duration (in minutes) of time per day where glucose values are within a hypoglycemic range (defined as < 54 mg/dL [3.0 mmol/L]) during the nighttime period.
- Percentage and Duration (in minutes) of time per day where glucose values are within a hypoglycemic range (defined as < 54 mg/dL [3.0 mmol/L]) during a 24-hour period.
- Incidence of hypoglycemic episodes during the nocturnal period and during a 24-hour period.
- Rate of hypoglycemic episodes per patient per year during the nighttime period and during a 24-hour period.
- Duration (in minutes) of each individual hypoglycemic episode.

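### SAP 4.11.2 applies one MMRM to every CGM variable, including episode incidence, episode rate and individual episode duration; these exploratory outcomes need models that match their data type.

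*SAP*

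**What the plan says.** SAP 4.11.2 opens with a single rule: "The following variables derived from CGM will be summarized and compared between treatment groups by visit using MMRM model". It then gives the terms: "The model will include the treatment, HbA1c stratum (<8.5% or ≥8.5%), baseline FBG, visit, and treatment by visit interaction". The reported contrast is the least-squares "mean difference between treatment groups will be summarized". No covariance structure is named.

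The list under that rule (SAP 4.11.2.1 to 4.11.2.4) is mostly percent time and variability measures. SAP 4.11.2.1 also contains three variables of other kinds:

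- a yes/no outcome, worded as "Incidence of hypoglycemic episodes during the nocturnal period and during a 24-hour period";
- a count over recording time, worded as "Rate of hypoglycemic episodes per patient per year during the nighttime period and during a 24-hour period";
- a measure taken once per event, worded as "Duration (in minutes) of each individual hypoglycemic episode".

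No other inferential model is given for them. SAP 4.11.1 mentions categorical measures only for descriptive statistics.

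Elsewhere the SAP does differently. Section 4.1 assigns MMRM to continuous repeated outcomes unless otherwise noted. Table BDCM.1 (SAP 4.10.3.2) analyses hypoglycemia rates by negative binomial regression with "log (exposure in year) as the offset in the model", and incidence by logistic regression, run only when at least 10 patients have the event. Both models include baseline SU use. Section 4.8 uses longitudinal logistic regression for HbA1c targets.

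Protocol 7.2 states that "the randomization will be stratified by country, baseline HbA1c (<8.5%, ≥8.5%), country, SU (yes/no), and baseline BMI (<30, ≥30"). Of these four distinct factors, the CGM model keeps only HbA1c.

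**The concern.** An MMRM expects one roughly continuous value per participant per visit and, as normally fitted, one variance shared by all arms. Each of the three variables breaks this in its own way.

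- **Incidence** is binary, so its variance is fixed by its mean.
- **Rate** is an overdispersed count over unequal recording time. SAP 4.11.2 itself says CGM records are lost when visit intervals exceed 4 weeks. An annualised rate without an offset gives a short and a long recording the same weight.
- **Individual episode duration** is neither binary nor a count. Its problem is the unit of analysis: a participant-visit may supply several durations or none, and the SAP does not say how they become one value.

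Protocol 3.2 names more frequent or longer hypoglycemia as the potential downside of a long-acting weekly insulin and relies on CGM for close monitoring. Protocol Table BDCM.2 lists duration and recurrence of hypoglycemic events as an exploratory endpoint. Intervals that are too short or too long on these outcomes would blur that readout.

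**Working it through.** The documents give no figure for this point, so there is none to reproduce.

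**Inputs from the documents.** Two-sided 90% intervals (SAP 4.1); three arms; about 100 completers per arm (protocol 10.1).

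**Assumptions.** Event probabilities, mean counts, negative binomial size k and intraclass correlation (ICC) are not in the documents. The calculation uses one visit, complete data, equal recording time, treatment as the only term, and one variance common to the arms. The common variance matches the SAP 4.7 example code, which has no arm-specific covariance; 4.11.2 is silent.

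**Formula.** Let vL be the variance in each LY arm, vD that in degludec, and n = 100 per arm. The model uses s² = (2vL + vD)/3.

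- One LY arm vs degludec: assumed variance 2s²/n; true variance (vL + vD)/n.
- Pooled LY vs degludec: assumed 1.5s²/n; true (vL/2 + vD)/n.
- Approximate coverage = 2Φ(1.645 × √(assumed/true)) − 1.

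For binary data v = p(1 − p); for counts v = μ + μ²/k.

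**Worked case.** Mean episodes 0.5 (LY) vs 1.5 (degludec), k = 0.3: vL = 0.5 + 0.25/0.3 = 1.333; vD = 1.5 + 2.25/0.3 = 9.0.

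- Pooled: assumed 1.333 + 4.5 = 5.833, true 0.667 + 9.0 = 9.667, √ratio = 0.777, coverage 79.9%.
- Single: assumed 7.778, true 10.333, √ratio = 0.868, coverage 84.6%.

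Simulation (40,000 runs) gives 79.4% and 84.2%. The other simulated results are:

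| LY / degludec | Single arm | Pooled |
|---|---|---|
| Incidence equal, 5% to 50% | 89.6–90.0% | 90.2–90.9% |
| Incidence 20% / 40% | 89.0% | 87.6% |
| Incidence 10% / 20% | 88.6% | 86.8% |
| Incidence 2% / 10% | 84.8% | 81.1% |
| Incidence 40% / 20% | 90.7% | 92.4% |
| Incidence 10% / 2% | 92.8% | 95.8% |
| Counts equal (k 0.2–0.5) | 90.0–90.3% | 89.9–90.3% |
| Counts 1 / 2 (k 0.3) | 85.5% | 82.0% |
| Counts 2 / 1 (k 0.3) | 92.3% | 94.7% |
| Counts 1.5 / 0.5 (k 0.3) | 93.0% | 95.7% |

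If only Algorithm 2 differs (1.5, with Algorithm 1 and degludec at 0.5), the Algorithm 1 vs degludec interval covers 99.1%, because the third arm inflates the common variance.

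With sensor time varying from 3 to 28 days (also assumed), pooled coverage is 86% at 10 vs 16 episodes per year and 85% at 3 vs 6. With the arms reversed it is 93% and 94%. Single-arm contrasts give 87–88% and 91–92%.

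**Matched models, Algorithm 1 vs degludec.** A log-link rate ratio with empirical standard error covers 88.5–88.9%. An odds ratio covers 89.7–90.4% at incidences of 10–40%, and 93.4% when an arm has 2–5%. At 2% vs 10%, an arm had no event in 13% of runs, so no estimate existed.

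**Duration, one row per episode treated as independent.** Assume a mean of 2 episodes and k = 0.5. The count variance is 2 + 4/0.5 = 10, so the size-weighted mean cluster is (10 + 4)/2 = 7 and the design effect is 1 + 6 × ICC. Type I error is approximately 2[1 − Φ(1.645/√design effect)]:

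| ICC | Design effect | Formula | Simulated (4,000 runs) |
|---|---|---|---|
| 0.05 | 1.3 | 14.9% | 15.6% |
| 0.1 | 1.6 | 19.4% | 18.6% |
| 0.2 | 2.2 | 26.7% | 25.9% |
| 0.3 | 2.8 | 32.6% | 31.4% |

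**Omitted stratum.** Take two balanced halves at 40% and 10% with no treatment effect. The model uses 0.25 × 0.75 = 0.1875; the within-stratum variance is (0.24 + 0.09)/2 = 0.165. Coverage is 2Φ(1.645 × √(0.1875/0.165)) − 1 = 92.1%; simulation gives 92.1% single and 91.8% pooled. The interval is slightly too wide, not too narrow.

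**The case against.** The strongest defence has five parts.

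1. **Section 4.1 allows exceptions.** MMRM is for continuous outcomes unless otherwise noted, and 4.11.2 could be such a note. That is formally possible, but no reason is given for treating CGM events differently from those in Table BDCM.1, and no exception resolves the undefined unit for duration.
2. **Intervals are not wrong in general.** A reader might infer that a normal model invalidates every binary or count comparison. The check does not support this: with about 100 per arm and equal rates in all arms, coverage is near 90%. The error appears only when arms differ, and it goes in both directions. If both LY arms have more episodes, which is the risk raised in protocol 3.2, intervals are too wide rather than too narrow.
3. **The largest shortfalls belong to the pooled contrast.** The SAP specifies pooling for HbA1c (4.7, 4.8), not for CGM. Single-arm coverage when LY has fewer events is milder, at 84% to 89%.
4. **Missing strata do not damage coverage.** A reader might blame the absence of SU, BMI and country for faulty intervals. Omission costs precision. Table BDCM.1 also leaves out BMI and country, so only SU has a consistency argument.
5. **The stakes are limited.** A reader might take this as undermining the trial's hypoglycemia evidence. CGM incidence and rate are exploratory (SAP 3.3, item 13). For the secondary hypoglycemia outcomes, documented and nocturnal events have negative binomial and logistic models, and severe-event incidence has Fisher's exact test.

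Points 2 to 5 stand and limit the finding. They do not remove the mismatch between model and outcome type.

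**Conclusion.** The point holds as a specification fault in exploratory analyses. SAP 4.11.2 assigns one MMRM with mean differences to a binary outcome, a rate and a per-episode measure, against the SAP's own practice.

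Under the assumed rates, coverage is near nominal when arms are equal. When both LY arms differ from degludec in the same direction, it is about 79% to 89% if LY has fewer events and 91% to 96% if LY has more. The cause is a common variance applied where variance follows the mean. For duration, analysing episodes as independent rows would give type I error of about 16% to 31% at a nominal 10%. The SAP does not say that it will do this; it leaves the unit open.

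These sizes rest on assumed event rates, dispersion and ICC, one visit, and a common covariance for all arms. The omitted strata are a matter of precision and consistency only. The primary HbA1c analysis is untouched.

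**What to change.** Amend SAP 4.11.2 as follows.

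- **Incidence:** logistic regression, keeping Table BDCM.1's condition of at least 10 patients with the event; otherwise report counts and percentages.
- **Rate:** negative binomial regression with log(valid sensor time) as offset.
- **Episode duration:** either one summary per participant (for example, mean duration, log-transformed) or an episode-level model that accounts for clustering within participant. Report how many participants contribute, since those without episodes supply no value.
- **Percent time and variability:** keep the MMRM.
- **Covariates:** add SU to the CGM models. BMI and country are optional where events are not sparse.

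The same edit should reconcile the periods in SAP 3.3, item 13 (0-12, 12-32 and 0-32 weeks) with the by-visit analysis in 4.11.

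The cost is SAP wording and, mostly, reuse of code already needed for Table BDCM.1, plus deriving valid sensor time. No new data are required.

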#### **Continuing Glucose Monitoring:**

A standard system will be used for continuing glucose monitoring (CGM) in an unblinded mode. The study participants will wear this device beginning on Day 0 at randomization, as shown in the Schedule of Activities (Section 2). In addition, all study participants will be allowed to use their blood glucose meters for additional blood glucose testing or for calibration of the CGM system if deemed necessary, or for taking self-monitored plasma glucose (SMPG) measurements during the outpatient period.

At the randomization visit (Visit 3), study participants will be trained on the use of the CGM device, CGM sensor replacement, interpretation of CGM based blood glucose values and alarms, and the requirements for CGM. For the first CGM session, study participants meeting all study-entry criteria will have the CGM sensor inserted as part of the Visit 3 activities.

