#### Study Participant Characteristics

[3a] Male study participants:

Men with female partners of childbearing potential must agree to use at least one effective method of contraception ([Appendix 5](#)) for the duration of the study and for at least 15 weeks (approximately 3 half-lives plus 90 days) following the last dose of IP.

[3b] Female study participants:

Women not of child-bearing potential may participate and include those who are:

- Infertile due to surgical sterilization (hysterectomy, bilateral oophorectomy, or tubal ligation), congenital anomaly such as Müllerian agenesis; or
- Postmenopausal, defined as:
  - A woman at least 50 years of age with an intact uterus, not on hormone therapy, who has had either:
    - a) Cessation of menses for at least 1 year, or
    - b) At least 6 months of spontaneous amenorrhea with a follicle-stimulating hormone  $>40$  mIU/mL (local laboratory); or
  - A woman 55 years or older not on hormone therapy, who has had at least 6 months of spontaneous amenorrhea; or
  - A woman at least 55 years of age with a diagnosis of menopause prior to starting hormone replacement therapy.

Women of childbearing potential must agree to remain abstinent (if this is their preferred and usual lifestyle), use 1 highly effective method of contraception, or a combination of 2 effective methods of contraception ([Appendix 5](#)) starting at screening and continuing for 15 weeks (approximately 3 half-lives plus 90 days) after the last dose of IP:

- Test negative for pregnancy at screening based on serum pregnancy test, followed by a negative urine pregnancy test within 24 hours prior to randomization (Visit 3)
- Not be breastfeeding

[4] Are at least 18 years of age at screening

[5] Have a baseline HbA1c value of 6.5% to 10%, inclusive, at screening

[6] Have been treated with a stable regimen of insulin glargine, insulin levemir or insulin degludec with or without OAM therapy for 3 months prior to screening and be willing to continue stable dosing throughout the study. Acceptable OAMs include up to 3 of the following:

- DPP-4 inhibitors
- SGLT-2 inhibitors
- biguanides
- alpha-glucosidase inhibitors
- sulfonylureas

Note: All OAMs must be used in accordance with the corresponding local product label at the time of screening.

[7] Have a body mass index (BMI) between 20 and 45 kg/m^2, inclusive with no significant weight gain or loss in the past 3 months ( $\geq 5\%$ )

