- Modifying analyses to ensure using the collected data as the input data (for example, CGM analyses using available baseline variables as covariates)

3. Study Objectives

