Baseline value for a variable is defined as the last nonmissing value for this variable prior to or at randomization visit (Visit 3), unless otherwise specified.

For continuous measurements, summary statistics will include sample size, mean, median, standard deviation (SD), minimum, and maximum. For certain variables that are considered to be log-normally distributed, the geometric mean and coefficient of variation (CV) will be provided instead.

For categorical measurements, summary statistics will include sample size, frequency, and percentages. Fisher's exact test will be used. Chi-squared test will be used for multi-category variables.

A mixed-model repeated measures (MMRM) model will be used for continuous outcomes with repeated postbaseline measurements to compare treatment arms, unless otherwise noted. Treatment comparisons will be performed for the treatment difference in least-squares means (LS mean). Means and LS mean by treatment group and visit, along with the standard error of LS mean, 90% CIs of the treatment differences along with the p-value for the treatment comparison will be displayed. For the change from baseline, p-value for the within-treatment comparison will also be displayed. For selected parameters, log-transformed values will be analyzed in the MMRM model instead. The actual, change from baseline and percentage change from baseline will be presented using the derivation based on the output from the MMRM model.

In this study, all negative binomial regression will estimate Group Mean instead of LS mean and use delta method to estimate the standard error of the Group Mean (Qu and Luo 2015). Group Mean is defined as the mean response in the treatment group for the studied population. The difference between LS mean and the Group Mean is that LS mean estimates the response by taking the inverse link function on mean covariates, while the Group Mean takes the inverse link function on individual patient covariates first and then averages over all patients.

All analyses will be implemented using SAS Enterprise Guide Version 7.1 or above.

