4.3. Patient Characteristics

Demographic and baseline characteristics including but not limited to age (years), age groups (<65 years, ≥65 years and <75 years, ≥75 years), sex, ethnicity, race, country, region, weight (kg), body mass index (BMI: kg/m²), BMI groups (<25, ≥25 and <30, ≥30 and <35, and ≥35 kg/m²), eGFR groups (estimated glomerular filtration rate based on the modified Modification of

Diet in Renal Disease [MDRD] equation: ≥ 90 , < 90 and ≥ 60 , < 60 and ≥ 30 , and < 30 mL/min/1.73 m²), duration of diabetes (years), baseline substance use (alcohol, drug, tobacco and caffeine baseline use status), baseline systolic blood pressure, baseline diastolic blood pressure, baseline HbA1c (% and mmol/mol), baseline HbA1c groups ($< 7\%$, $\geq 7\%$ and $< 8.5\%$, $\geq 8.5\%$), fasting serum glucose (FSG: mmol/L and mg/dL), lipid measures (triglycerides, FFA, total cholesterol, HDL-C, and LDL-C), liver enzymes (ALT, AST and total bilirubin), HbA1c strata (HbA1c $< 8.5\%$ and $\geq 8.5\%$ at Visit 1), and sulfonylureas [SU] use will be summarized by treatment group using the All Randomized Population. Continuous measures will be summarized using descriptive statistics and treatment difference will be analyzed using the analysis of variance. Categorical measures will be summarized using sample size, frequency, and percentage and treatment difference will be analyzed using Chi-squared test. The by-patient listing of demographic and selected baseline characteristics will be provided for all randomized patients.

Number of randomized patients and number of patients discontinued per investigator within country for each treatment group will be summarized. In addition, number of enrolled patients per investigator within each country will also be summarized.

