4.8. Secondary and Additional Efficacy Analyses

The analysis population for the secondary analysis on HbA1c reduction is the EAS. Treatment comparison at 32 weeks will be used to assess the difference between the pooled LY arm and Degludec arm. The 2-sided 90% CI for the LS mean of the difference between pooled LY arm and Degludec arm in the change in HbA1c at 32 weeks will also be constructed.

A sensitivity analysis will be conducted to evaluate the “treatment policy” estimand, which is defined as the treatment differences in HbA1c at 32 weeks with the randomized treatment based

on all randomized patients who took at least one dose of study medication, and have baseline and at least one postbaseline measurement. In this analysis, all endpoint data regardless of treatment disposition status will be included and missing data will be imputed using multiple imputations to assess sensitivity to departures from the missing at random assumption. More specifically, the missing endpoint will be imputed multiple (for example, 100) times using the baseline data. Then, the inference based on the multiple imputations framework will be used (Rubin 1987).

The following secondary and additional efficacy analyses will be performed based on the EAS using the same MMRM model as the primary analysis with the addition term of HbA1c strata (<8.5% and \geq 8.5%) for non-HbA1c measures:

1. HbA1c change from baseline to Week 12;
2. Fasting blood glucose (FBG) by SMBG and change from baseline at Weeks 12 and 32;
3. Fasting serum glucose (FSG) by laboratory and change from baseline at Weeks 6, 12, 18, and 32;
4. Between-day glucose variability measured by the SD of the FBG (SMBG) at Week 12 and 32;
5. Six-point SMBG profile (pre-meal and 2-hour postprandial SMBG measurements for the morning, midday, and evening meals in 1 day) at Weeks 12 and 32. Since the baseline SMBG profile is not collected, the baseline FBG instead of baseline value of the dependent variable will be used as a covariate.
6. Within-day and between-day glucose variability measured by the standard deviation (SD) of 6-point SMBG. Since the baseline SMBG profile is not collected, the baseline SD of FBG instead of baseline value of the dependent variable will be adjusted as a covariate.

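### The CGM model takes baseline HbA1c only as a two-level stratum beside baseline FBG; adding the measured value could modestly sharpen these exploratory comparisons

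*SAP*

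**What the plan says.** SAP 4.11.2 fits one MMRM to the CGM variables: "The model will include the treatment, HbA1c stratum (<8.5% or ≥8.5%), baseline FBG, visit, and treatment by visit interaction". It lists no other baseline covariate.

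A CGM baseline cannot exist. Protocol 5.1.1 states: "The study participants will wear this device beginning on Day 0 at randomization". The SAP Revision History gives the intent behind the covariates, citing "CGM analyses using available baseline variables as covariates" as an example of fitting the analyses to the data collected.

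Measured HbA1c is one of those variables. Protocol 6.1 requires it for entry ("Have a baseline HbA1c value of 6.5% to 10%, inclusive, at screening"), and the Schedule of Activities lists it at Visits 1 and 3. SAP 4.1 defines baseline as the latest available value up to Visit 3, whereas SAP 4.3 takes the stratum from Visit 1.

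Other SAP models use baseline HbA1c itself rather than the stratum:
- the primary MMRM (4.7)
- the HbA1c-target logistic model (4.8)
- the hypoglycemia models in Table BDCM.1 (4.10.3.2), for example "Negative binomial regression with treatment, baseline SU use (yes/no), baseline HbA1c, baseline hypoglycemia event rate"

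The six-point SMBG outcomes in SAP 4.8 also lack their own baseline. For the profile, "the baseline FBG instead of baseline value of the dependent variable will be used as a covariate". For SMBG variability, the substitute is the baseline SD of FBG. Both models add the HbA1c stratum and carry the primary model's country, BMI and sulfonylurea terms.

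Neither document says why measured HbA1c is left out of the CGM model.

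**The concern.** Without a baseline of the outcome, precision depends on how well the substitute covariates predict it. Laboratory HbA1c summarizes prior glycemia over weeks, while FBG reflects one time of day. Cutting HbA1c at 8.5% discards the variation within each side of the cut, and entry spans 6.5% to 10%. Any of that variation which predicts time in range, and which FBG does not already carry, stays in the residual. The treatment comparison then has a wider confidence interval than the collected data would allow.

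The stake is limited. Time in range and the other CGM measures are exploratory in both documents (Protocol Table BDCM.2; SAP 3.3), and no power target or decision rule depends on them.

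**Working it through.** **The plan's own figure.** The documents state no precision for any CGM variable. The only related figure is the primary power in Protocol 10.1: margin 0.4, SD 1.1, true difference 0, 200 pooled versus 100, two-sided alpha 0.10.
- SE = 1.1 × √(1/100 + 1/200) = 0.1347
- 0.4/0.1347 − 1.645 = 1.324, which gives power of 90.7%

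The stated 90% reproduces, and the CGM covariates do not affect it.

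**Method for CGM.** HbA1c, FBG and time in range were simulated as jointly normal, with HbA1c truncated to the 6.5–10% entry range. Two residual variances were compared: V_s with the 8.5% stratum plus FBG, and V_m with measured HbA1c plus FBG. Interval width scales with the square root of residual variance, so the narrowing from using the measured value is 1 − √(V_m/V_s).

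**Assumptions (none is in the documents).** Before truncation, HbA1c mean is 7.7–8.3 and SD 0.8–1.0. Correlation of time in range with HbA1c is −0.2 to −0.6, and with FBG −0.2 to −0.5. Correlation of HbA1c with FBG is 0.2 to 0.6.

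**Information lost by the cut.** The stratum correlates 0.71 to 0.81 with measured HbA1c. It therefore misses 1 − 0.81² = 34% to 1 − 0.71² = 50% of the HbA1c variance, before FBG recovers any of it.

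**Middle case** (HbA1c mean 8.0, SD 0.8; correlations −0.4 with HbA1c, −0.3 with FBG, 0.4 between the two):
- V_s = 0.8535 and V_m = 0.8182, ratio 0.9587, so variance is 4.1% lower
- 1 − √0.9587 = 2.1% narrower interval
- 1/0.9587 = 1.043, equivalent to about 4% more patients
- Without FBG in either model, the variance reduction would be 1 − 0.8419/0.8956 = 6.0%, so FBG already recovers part of the loss
- With the stratum and the measured value both in the model, residual variance is again 0.8182, so keeping the stratum does no harm

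**Whole grid, by correlation of HbA1c with time in range:**

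| Correlation | Variance reduction | Interval narrower by |
|---|---|---|
| −0.2 | 0 to 1.2% | 0 to 0.6% |
| −0.3 | 0 to 2.9% | 0 to 1.5% |
| −0.4 | 0.7 to 6.6% | 0.3 to 3.3% |
| −0.5 | 3.0 to 12.9% | 1.5 to 6.7% |
| −0.6 | 6.9 to 22.7% | 3.5 to 12.1% |

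The grid medians are 3.5% for variance and 1.8% for interval width.

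**A narrower set of assumptions.** Here the correlations with time in range are −0.25 to −0.5 for HbA1c and −0.2 to −0.35 for FBG, HbA1c with FBG is 0.45, HbA1c mean is 8.0–8.2 and SD 0.9–1.0. V_s/V_m is then 1.016 to 1.093. The planned intervals are √1.016 − 1 = 0.8% to √1.093 − 1 = 4.5% wider than with the measured value.

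**Limits.** The simulation assumes a linear relation and one generic outcome. It cuts the same HbA1c reading that it uses as the measured value, whereas the SAP takes the stratum from Visit 1 and baseline from up to Visit 3. Glucose variability, hypoglycemia-range and SMBG outcomes were not simulated.

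**The case against.** The strongest defense is that nothing here is an error. The stratum is a randomization factor (Protocol 7.2). Using it for outcomes other than HbA1c is the documents' general convention (Protocol 10.3.3.2 and 10.3.4; SAP 4.8). The endpoints are exploratory and the likely gain is about 2% of interval width. On-treatment glucose is also driven by titration to fasting glucose (Protocol 7.2.1.2, Appendix 7), which could weaken the link between baseline HbA1c and later time in range. All of that stands. It makes the point small, but shows no cost or drawback to adding the covariate.

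Several stronger readings are tempting, and the documents do not support them:
- **A reader might infer that everyone from 6.5% to 8.4% is treated as identical.** That is so only for HbA1c; baseline FBG still separates participants within a stratum.
- **A reader might infer that every CGM interval is too wide.** That is conditional on HbA1c predicting the variable within strata beyond FBG. At the weak end of the grid the gain is zero.
- **A reader might infer that HbA1c imbalance within a stratum biases the comparison.** Randomization prevents systematic imbalance, FBG corrects part of any chance imbalance, and what remains is the imprecision already counted above.
- **A reader might convert the loss into a share of the 375 randomized.** That base is too large. The CGM Population requires a dose and CGM data (SAP 4.1), SAP 4.11.1 refers to selected sites and censors data after discontinuation, SAP 4.11.2 notes gaps when visits are more than four weeks apart, and Protocol 10.1 plans 300 completers.
- **A reader might equate the SMBG models with the CGM model.** Their substitute baselines differ from each other, and both carry country, BMI and sulfonylurea terms that the CGM model lacks.

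**Conclusion.** The point holds as a minor improvement in efficiency. The CGM model uses a coarsened form of a covariate that the trial measures in everyone and that the SAP uses as a value elsewhere, although these outcomes have no baseline of their own. The expected cost is an interval roughly 0 to 5% wider than necessary, about 2% in the middle case. Only at the extreme of the grid (correlation −0.6) would the measured value narrow it by as much as 12%. These figures rest entirely on assumed correlations and a linear relation. Bias, type I error, the primary analysis and the sample size are not affected.

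**What to change.** In SAP 4.11.2, add baseline HbA1c as a continuous covariate, using the SAP 4.1 baseline (latest value up to Visit 3). Keep the HbA1c stratum, since it is a randomization factor, and keep baseline FBG.

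The same addition can be made in SAP 4.8 to the six-point SMBG profile model (now baseline FBG plus HbA1c strata) and the SMBG variability model (now baseline SD of FBG plus HbA1c strata). No size was computed for these.

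The cost is one term and one degree of freedom per model, with no new data. The study is open-label and the CGM analyses have no multiplicity adjustment, so the covariate should be written into the SAP before database lock and not chosen after results are seen.
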